11 EFFICACY ANALYSES

This section details the specifications for summarizing efficacy endpoints.

The primary and key secondary efficacy analyses will be performed on the ITT, mITT, and PP populations. The primary analysis population is the mITT population. Exploratory efficacy analyses will be performed on the ITT and ITT-2nd Dose populations, depending on the endpoint. Efficacy responses will also be presented in a listing.

Unless otherwise stated, all primary, secondary, and exploratory efficacy hypotheses will be tested using a logistic regression model with treatment group and background use of medication to reduce the frequency of migraine episodes as covariates. For treatment comparisons, an estimate of the odds ratio of achieving a response, as well as the corresponding confidence interval and p-value using Wald's test, will be computed. Tests of the primary and key secondary endpoints will be conducted at a one-sided significance level of 0.025; tests of all other endpoints will be conducted at a two-sided significance level of 0.05.

Analyses of second-dose endpoints with too few subjects in the treatment-sequence-subpopulation groups may have too little data separation for a logistic regression model to reach a stable solution. For these models, the "Firth" modification of the maximum likelihood estimation will be used to achieve a solution.

The efficacy endpoints will depend on data collected by e-diary that depends on subject's response entry in the correct order and at the expected scheduled e-diary assessment times. Assessment times are analyzed as calculated by the e-diary and not as part of analysis programming.

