4.3 Examination of subgroups

Subgroup analyses will be conducted as stated in the exploratory analyses section. It should be noted that the study was not designed to detect treatment differences with high statistical power within subgroups.

The following subgroups will be assessed and are classified as follows:

- Subjects with any triptan use within three months of screening.
- Subjects that dosed a migraine greater than 4 hours after migraine start.
- Subjects with either Topamax or Propranolol use while on study.
- Subjects with Topamax use while on study.
- Subjects with Propranolol use while on study.
- Subjects with one or more cardiovascular risk factors (CVRF)
- Subjects with treatment emergent adverse events (TEAE) of dizziness

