5.2 Analysis of First and Second Doses

Any analyses based on first dose will only include data observed up to the time of dosing with a second dose. These summaries will be presented based on the first dose taken. The exception to this is the primary and secondary endpoints at the 2-hour time point; if a second dose is taken before the 2-hour time point, the subject will still be included in the summary at 2 hours and will be analysed as having not achieved headache pain-free or MBS-free status at 2 hours.

Any analyses based on the second dose will only include data observed on or after the time of dosing with a second dose. These summaries will be presented by treatment sequence, listed in Section 2.3. Analyses based on the second dose will be done for both the rescue and recurrence subpopulations.

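### SAP 11 moves sparse second-dose logistic models to Firth estimation but names no matching test or interval, so the default Wald inference applies and is conservative in small recurrence groups

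*SAP*

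**What the plan says.** SAP 11 sets one default for all efficacy testing: "Unless otherwise stated, all primary, secondary, and exploratory efficacy hypotheses will be tested using a logistic regression model". The model has "treatment group and background use of medication to reduce the frequency of migraine episodes as covariates". The odds ratio is estimated, "as well as the corresponding confidence interval and p-value using Wald's test, will be computed". Endpoints other than the primary and key secondary ones are tested at two-sided 0.05.

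The next paragraph makes an exception: "Analyses of second-dose endpoints with too few subjects in the treatment-sequence-subpopulation groups may have too little data separation" for the model to reach a stable solution, and for these the Firth "modification of the maximum likelihood estimation will be used to achieve a solution". That exception concerns estimation only. No p-value or interval method is attached to it.

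SAP 5.2 requires the second-dose results to be split: "Analyses based on the second dose will be done for both the rescue and recurrence subpopulations". Under SAP 4.1 the recurrence group holds only subjects who were pain-free at 2 hours, recurred, and took a second dose within 24 hours of the first. SAP 5.1 calls all second-dose analyses exploratory. The statistical section of the protocol synopsis promises exploratory second-dose comparisons between treatment groups.

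**The concern.** Firth's penalty keeps the odds ratio finite when a group has no responders. It does not make the normal approximation behind a Wald test accurate in that situation. The estimate sits near the edge of the parameter space, its standard error is large, and the penalised likelihood is strongly asymmetric, whereas the Wald interval is symmetric on the log-odds scale. The inference that matches a penalised fit comes from the penalised likelihood itself: a likelihood-ratio p-value and a profile interval.

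The effect of a second dose in rescue and recurrence is a stated additional objective (protocol 5.3). If the recurrence test rejects far less often than its nominal level, a non-significant result could be read as no benefit when the test statistic is part of the reason.

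**Working it through.** **The plan's own figure.** SAP 2.2 states more than 90% power for pain-free at 2 hours with 570 per arm, one-sided 0.025. Two-proportion power at 7.4% v 18.8%, 13.6% and 13.9% is 99.99%, 92.8% and 94.6%, so the statement reproduces. The documents give no power or error rate for any second-dose analysis.

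**Recurrence group sizes.** Inputs from the documents: 570 per arm; pain-free 7.4% on placebo and 18.8% on 200 mg (SAP 2.2); second dose active or placebo 2:1 within each active arm, read from the table in SAP 2.3.

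- Pain-free on placebo: 570 × 0.074 = 42.
- Pain-free on 200 mg: 570 × 0.188 = 107. Of these, 380 × 0.188 = 71 are assigned active as second dose and about 36 placebo.
- The share who recur and redose is not in the documents. Assuming 15%, 25% or 40%, 200 mg/200 mg v placebo/placebo is about 11 v 6, 18 v 10 and 29 v 17.
- Within the 200 mg arm, 10% to 40% gives about 7 v 4 to 29 v 14 (second dose active v placebo).

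**Formulas (two groups, no covariate).** The Firth estimates are p = (x + 0.5)/(n + 1) per group, β is the difference in logits, and SE² = Σ 1/[n p(1 − p)]. Wald uses z = β/SE. The penalised likelihood ratio (PLR) is twice the difference in log L + ½ log|I| between the fitted model and β = 0, on chi-square with 1 df. At β = 0 the common rate is (x₁ + x₀ + 1)/(n₁ + n₀ + 2).

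**Example, 9/18 v 0/9.**

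- p₁ = 9.5/19 = 0.50; p₀ = 0.5/10 = 0.05; odds ratio 19; β = 2.944.
- SE = √[1/(18 × 0.25) + 1/(9 × 0.05 × 0.95)] = √(0.222 + 2.339) = 1.600.
- Wald: z = 1.84, p = 0.066, 95% CI 0.82 to 438.
- PLR: the null rate is 10/29 = 0.345; the penalised log-likelihoods are −12.611 and −16.138; statistic 7.05, p = 0.008.
- Fisher's exact p = 0.012.

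For 10/20 v 0/10 the p-values are 0.054 (Wald), 0.005 (PLR) and 0.011 (Fisher). In both examples Fisher's test agrees with PLR rather than with Wald.

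**Exact enumeration, two-sided 0.05, no covariate.** Size is the range over common response rates of 10% to 50%. Power assumes 50% v 5%.

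| Groups | Wald size | PLR size | Wald power | PLR power |
|---|---|---|---|---|
| 11 v 6 | 0.1–1.2% | 0.6–4.0% | 9% | 39% |
| 18 v 10 | 0.3–2.5% | 1.7–4.8% | 38% | 78% |
| 29 v 17 | 0.6–3.8% | 4.1–5.7% | 88% | 95% |

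**With the SAP covariate** (simulation, 3,000 trials, 20% preventive use assumed), at 50% v 7.4%: 10% v 45% at 14 v 7, 35% v 70% at 20 v 10, and 76% v 88% at 30 v 15 (Wald v PLR). The result does not depend on leaving the covariate out, and these 2:1 sizes correspond to the active v placebo second-dose comparison within an arm.

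**Where the difference fades.** At 60% v 30%, 18 v 10, power is 23% v 33%. In groups of 150 v 75 (assumed rescue size, with covariate) it is 67% v 72% at 20% v 7.4%, and 32% v 35% at 30% v 20%.

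**Confirmatory tests.** With 570 per arm and 7.4% in both arms, the one-sided Wald test at 0.025 rejects 2.4% of the time. It is well calibrated there.

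**The case against.** Several objections stand in part.

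- **Wald with Firth is inferred.** A reader might take it that the SAP deliberately chose Wald for the Firth models. It does not say so; Wald applies only because nothing else is stated. If something else was intended, the SAP is silent on it, and the same sentence is needed.
- **Little second-dose testing is spelled out.** SAP 11.7.13, 11.7.15 and 11.7.17 describe counts and percentages, protocol 10.6 describes summary statistics, and no contrast is named. The Firth sentence has no purpose unless models are fitted, and the protocol synopsis promises comparisons. The choice of contrast here is still an assumption. Placebo/placebo v 200 mg/200 mg among recurrers is not a clean randomised comparison, because both groups are selected on first-dose response.
- **The largest gains need a low comparator rate.** Recurrers have already responded once and may redose at mild pain, so higher rates are plausible. At 60% v 30% both tests are weak.
- **The error is conservative.** It produces no false claim, and a table showing 0/9 v 9/18 would still be visible to any reader.

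Stronger readings are tempting but not supported:

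- *The strongest contrasts are rejected least.* This is false for Firth. Against 0/9, Wald z rises from 1.84 at 9/18 to 2.24, 2.69 and 3.09 at 12, 15 and 18 of 18.
- *The PLR test never exceeds its nominal level.* It reaches 5.7% at 29 v 17 with a common rate of 20%.
- *The drug-use subgroups have the same fault.* For groups such as "Subjects with Propranolol use while on study", SAP 11.8 plans summary tables and states no subgroup hypothesis. SAP 4.3 already warns of low power there.

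**Conclusion.** The point holds as a limited one. By default, SAP 11 leaves Wald inference on Firth-fitted second-dose models, and in small recurrence groups with zero or few responders that test is markedly conservative. Its size is about 0.1% to 2.5% at 11 v 6 and 18 v 10. At an assumed 50% v 5%, the power given up relative to PLR is about 30 points at 11 v 6, 40 points at 18 v 10 and 7 points at 29 v 17. At 60% v 30% and 18 v 10 it is about 10 points, and in rescue-sized groups about 3 to 5 points.

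These figures rest on assumed redosing shares, second-dose response rates and preventive-medication use. The direction does not depend on those choices in the cases run; the size does. The conclusion is that real effects in small recurrence groups are more likely to be missed, not that they will be missed.

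Only binary second-dose endpoints are concerned. Disability and global impression use Cochran-Mantel-Haenszel tests, and the time-to-event endpoints use Kaplan-Meier. All second-dose analyses are exploratory and outside the sequence in SAP 11.1, so no confirmatory conclusion changes. This is a cheap improvement of low priority.

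**What to change.** Add after the Firth sentence in SAP 11:

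> For every model fitted with the Firth modification, 95% confidence intervals will be profile penalised-likelihood intervals and p-values will be from the penalised likelihood-ratio test, in place of Wald.

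The p-value should be computed with the treatment coefficient held at zero and the penalty taken from the full model, so that it agrees with the profile interval. Keep Wald for the six confirmatory tests.

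The cost is one sentence and a small change to the logistic regression program. No new data are needed and no confirmatory result is touched. The one drawback is that sparse exploratory tables will carry a different interval type from the main tables, which a footnote should state. The change should be made before unblinding, so that the test is not chosen with results in view.

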11.1 Multiplicity Adjustment

The gatekeeping procedure will be implemented to prevent Type I error inflation for multiple comparisons among the primary and secondary analyses. The primary efficacy endpoint will be tested first. If the primary analysis is statistically significant (one-sided $p < 0.025$), additional confirmatory hypotheses will be tested sequentially, in the following order:

1. Treatment comparison, between lasmiditan 200 mg and placebo, as measured by subjects who

- are MBS-free at 2 hours post-dose.
2. Treatment comparison, between lasmiditan 100 mg and placebo, as measured by subjects who are headache pain-free at 2 hours post-dose.
 3. Treatment comparison, between lasmiditan 100 mg and placebo, as measured by subjects who are MBS-free at 2 hours post-dose.
 4. Treatment comparison, between lasmiditan 50 mg and placebo, as measured by subjects who are headache pain-free at 2 hours post-dose.
 5. Treatment comparison, between lasmiditan 50 mg and placebo, as measured by subjects who are MBS-free at 2 hours post-dose.

If one of the analyses is not statistically significant, then all subsequent analyses will be exploratory rather than confirmatory.

11.2 Primary Efficacy Analysis

The primary efficacy analysis will test the treatment effect, between lasmiditan 200 mg and placebo, of the primary efficacy endpoint of the proportion of subject's headache pain-free at 2 hours post-dose. This analysis will be presented by treatment group, based on the first dose.

Headache pain-free is defined as a reduction in headache severity from mild (1), moderate (2), or severe (3) at baseline to none (0).

Subjects who do not provide a headache pain severity rating at baseline, or who do not provide a headache pain severity rating at the two-hour time point will be assumed to have not achieved headache pain-free.

Subjects taking any rescue medication within the first two hours will be assumed to have not achieved headache pain-free. Subjects who use other medication prior to the study drug to treat the migraine attack will also be assumed to have not achieved headache pain-free.

Subjects who treat a no (0) severity migraine will not be included in the primary analysis. Sensitivity analyses, as described in Sections 11.4, 11.5 and 11.6 will also be performed for the primary endpoint on the mITT population.

11.3 Key Secondary Efficacy Analysis

The key secondary efficacy analyses will test the following:

- The treatment effect, between lasmiditan 200 mg and placebo, of the key secondary efficacy endpoint of MBS-free at 2 hours post-dose.
- The treatment effect, between lasmiditan 100 mg and placebo, of the key secondary efficacy endpoint of headache pain-free at 2 hours post-dose.
- The treatment effect, between lasmiditan 100 mg and placebo, of the key secondary efficacy endpoint of MBS-free at 2 hours post-dose.
- The treatment effect, between lasmiditan 50 mg and placebo, of the key secondary efficacy endpoint of headache pain-free at 2 hours post-dose.
- The treatment effect, between lasmiditan 50 mg and placebo, of the key secondary efficacy endpoint of MBS-free at 2 hours post-dose.

MBS-free is defined as the absence of the associated symptom of migraine (either nausea, phonophobia, or photophobia) at 2-hour post-dose that was identified pre-dose as the most bothersome symptom. Subjects who record that no symptoms were present at baseline will be

excluded from the key MBS analyses. Likewise, subjects who treat a migraine of no (0) severity will not be included in the key analysis of headache pain. Such subjects will also be excluded from the table produced for the sensitivity analysis described in Section 11.5, but not from the programming steps that impute missing MBS data.

Subjects who do not provide a symptom rating at baseline will be considered as follows:

- Subjects who record at least one symptom present at baseline, but who do not designate one as most bothersome, will be treated as if all symptoms present are most bothersome and will be considered MBS-free at any time point post-dose only if all symptoms present at baseline are no longer present at that time point.

Subjects taking rescue medication within the first two hours, or who fail to record a symptom rating at 2 hours, will be assumed to have not achieved MBS-free. Subjects who use other medication prior to the study drug to treat the migraine attack will also be assumed to have not achieved MBS-free.

The counts and percentages of which symptom was chosen as the most bothersome symptom will also be presented.

These analyses will be presented by treatment group, based on the first dose.

Sensitivity analyses, as described in Sections 11.4, 11.5 and 11.6 will also be performed for the key secondary endpoints on the mITT population.

11.4 Sensitivity Analysis of Primary and Key Secondary Endpoint for Corrected Stratum

While randomizing subjects in the study, subjects were to be stratified (yes or no) for use of prophylactic medications that prevent or reduce the frequency of migraine episodes. In the event of mis-stratification occurring while randomizing these subjects, the primary and key secondary analyses will be redone using stratification as corrected in the course of data review. The data for headache pain free and MBS free at 2-hour post dose will be analyzed as described in Sections 11.2 and 11.3, but using the corrected stratifications.

11.5 Sensitivity Analysis of Primary and Key Secondary Endpoints for Missing Data

The proposed primary method of handling missing data that considers subjects with missing data at 2 hours as non-responders may be regarded as not conservative if the proportion of subjects with missing data at 2 hours is greater in the placebo arm than in the lasmiditan arms. To address the possibility of this scenario, headache severity score/MBS presence at 2 hours will be imputed under the following assumptions.

Missing data for subjects from the placebo arm will be imputed under the assumption of the missing at random (MAR) mechanism, where these subjects are assumed to have unobserved values in line with similar placebo subjects with available data, taking into account their values observed prior to time points with missing data. For subjects from the lasmiditan arms, monotone missing data (missing from a given time point through 2 hours) will be imputed from the MAR-based imputation model that was estimated from the placebo subjects, assuming that the lasmiditan subjects with missing data will drift towards the mean response of the placebo arm. This approach is likely to result in more favorable imputations for the placebo arm compared with the non-responder assumption, while for the lasmiditan arms it will not assume a treatment effect beyond the study effect. This approach will be more conservative than the primary analysis if the proportion of subjects dropping out is greater in the placebo arm than in the lasmiditan arms.

This approach will be implemented with multiple imputation (using PROC MI in SAS v9.4) as described in the following 3 steps.

- Early rescue. Subjects taking any rescue medication within the first two hours will be assumed to have the worst possible value (i.e., headache severity = 3/MBS still present) for all time points up to 2 hours (missing or not) after the intake of rescue medication.
- Establish monotone missing pattern. Intermediate missing data will be imputed under the MAR assumption within each treatment arm using a Fully Conditional Specification (FCS) method using a logistic regression imputation model with variables for treatment group, background use of medication to reduce the frequency of migraine episodes, baseline headache severity score, baseline MBS, pain severity score, and MBS presence at all time points. Five hundred imputations will be generated. The seed to start the random number generator will be 416713. Only imputations for intermediate missing values will be retained from this step. The remaining (monotone) missing data will be imputed as described below.

To accomplish this, original data with missing values will be reconfigured to a “horizontal” data set wherein missing data are to be imputed. Consistent with the table to be generated, treatment sequences will be combined by the first dose in each sequence. It will include assessments of headache severity and MBS free. Each subject will have one observation and 1 response variable for headache severity at each time point and 1 response variable for MBS at each time point. (e.g., HAsev_0, HAsev_1,..., HAsev_8, MBS_0, MBS_1, ..., MBS_8). Original headache severity ratings will be kept in the reconfigured data and reduced to pain-free, or not, at the step where analysis models are run. An entered assessment of no MBS at the time of dosing will be kept in the reconfigured data and that result of no MBS will be propagated to the last assessment time for which a subject also has headache-pain assessments.

The PROC MI procedure will be used to fill in the missing data to get “monotone missing pattern,” using code of this general form:

```
proc mi data = horizontal
    out = monotone
    nimpute=500
    seed = 416713
    ;
var trtp cmuse2fl HAsev_0 MBS_0 HAsev_1 MBS_1 HAsev_2 MBS_2 HAsev_3 MBS_3
    ... HAsev_8 MBS_8;

class trtp cmuse2fl HAsev_0 MBS_0 HAsev_1 MBS_1 HAsev_2 MBS_2 HAsev_3 MBS_3
    ... HAsev_8 MBS_8;

FCS LOGISTIC;

run;
```

- MAR-based placebo model. Data partially imputed on previous steps will then be used together with observed data for the estimation of the MAR-based model from the placebo arm, which will be done using a sequential logistic regression imputation model (Ratitch et al, 2013). The seed to start the random number generator will be 482112.

The MAR-based placebo imputation model for headache severity score as well as for MBS presence will be estimated based on data from placebo subjects and will include background use of medication to reduce the frequency of migraine episodes, baseline headache severity score, baseline MBS, pain severity score, and MBS presence at the previous time point before the one being imputed as explanatory variables. The placebo treatment group value will be set to make it the reference value. Missing values of headache severity score and MBS presence in all treatment arms will then be imputed from this single placebo imputation model.

For this step, PROC MI will be run second time with a BY variable that identifies the individual imputations from the previous steps. Code will have this form.

```
proc mi data = monotone_post
/* "monotone_post" contains data after a post-processing step above, in which imputed
values were retained for only the original intermediate missing values (those not originally
fitting the monotone missing pattern). */

    out = imputed_all
    nimpute = 1
    seed = 482112
    ;
    by _imputation ;

/*Note: treatment variable in the CLASS statement for compatibility with the MNAR
statement*/

CLASS trtp cmuse2fl HAsev_0 MBS_0 HAsev_1 MBS_1 HAsev_2 MBS_2 HAsev_3
MBS_3 HAsev_4 MBS_4;

var cmuse2fl HAsev_0 MBS_0 HAsev_1 MBS_1 HAsev_2 MBS_2 HAsev_3 MBS_3
HAsev_4 MBS_4;

/*MONOTONE LOGISTIC statement and MNAR statement will be added for each imputed
variable as below */

monotone logistic (HAsev_1 = cmuse2fl HAsev_0 MBS_0);
monotone logistic (MBS_1 = cmuse2fl HAsev_0 MBS_0 );
monotone logistic (HAsev_2 = cmuse2fl HAsev_0 MBS_0 HAsev_1 MBS_1);
monotone logistic (MBS_2 = cmuse2fl HAsev_0 MBS_0 HAsev_1 MBS_1);

...

monotone logistic (HAsev_4 = cmuse2fl HAsev_0 MBS_0 HAsev_3 MBS_3);
monotone logistic (MBS_4 = cmuse2fl HAsev_0 MBS_0 HAsev_3 MBS_3);

mnar model(HAsev_1 / modelobs=(trtp='0'));
mnar model(MBS_1 / modelobs=(trtp='0'));

...
```

```
mnnar model(HAsev_4 / modelobs=(trtp='0'));
mnnar model(MBS_4 / modelobs=(trtp='0'));

run;
```

Headache pain-free status and MBS-free status will then be computed from the multiple imputed data. The multiple imputed datasets will be analysed using the same methods as in the primary or secondary analysis for each imputation created above, followed by combining the results using Rubin's rule (Rubin, 1987). Odds ratios and the corresponding standard error estimates obtained from analysis of each imputed dataset will be log-transformed before applying Rubin's combination rule. The combined estimate and confidence limits will then be exponentiated to obtain the combined odds ratio and confidence interval.

For this purpose, proportions of responders and confidence intervals about those proportions will be estimated for each imputation and treatment group using the FREQ procedure. Those estimates will then be combined using the MIANALYZE procedure, using code of this form:

```
*** Combine proportion estimates of responders in each treatment arm;
PROC SORT DATA=prop_trtp
  BY trtp _Imputation_
RUN;

PROC MIANALYZE DATA=prop_trtp ;
  MODELEFFECTS prop ;
  STDERR prop_se ;
  BY trtp ;
  ODS OUTPUT PARAMETERESTIMATES=mian_prop_trtp ;
RUN ;
```

Such data for proportion of headache pain free and MBS free will be presented only up to 2-hour time points.

For the hypothesis test and odds ratio at 2 hours, parameter estimates and confidence intervals about the parameters will be produced using the LOGISTIC procedure for each imputation created in PROC MI. The predictor variables in the LOGISTIC model will include treatment group and stratification value. The estimates will then be combined using the MIANALYZE procedure in a step of this form:

```
PROC MIANALYZE PARMS(CLASSVAR=CLASSVAL)=lgsparms ;
  CLASS trtp cmuse2fl ;
  MODELEFFECTS trtpn ;
  ODS OUTPUT PARAMETERESTIMATES=mian_ ;
RUN ;
```

Odds ratios and corresponding confidence intervals will be calculated by exponentiating the combined parameter estimates.

Additionally percent of subjects with missing data to be imputed, and percent of data points imputed at each times before 2 hours will be summarized for headache pain free and MBS free.

11.6 Sensitivity analysis of Primary and Key Secondary Endpoint by removal of subjects due to complex e-diary data

As described in the Section 5.4, #6b, #8 and #9, some complex e-diary data issues may lead some subjects to be included in the original efficacy analysis of primary and key secondary endpoint under some listed assumptions. To these assumptions, the primary and key secondary efficacy analyses will be redone by removing these subjects. The data for headache pain free and MBS free at 2-hour post dose will be analysed as described in Sections 11.2 and 11.3, but by removing these subjects in the described section.

